8.4.2. Diaphragm Movement

- a. Prior to the first PFA application, the Investigator must confirm absence of pre-existing hemidiaphragmatic paralysis.

8.4.3. Peri-procedural Anticoagulation

- a. Heparin should be administered prior to (or immediately following) transseptal puncture during AF ablation procedures and adjusted to achieve and maintain a target ACT of at least 350 seconds. ACT should be checked approximately every 15-30 minutes.
- b. Performance of AF ablation in a subject systemically anticoagulated with VKA or novel oral anticoagulants (NOACs) does not alter the need for intravenous heparin to maintain a therapeutic ACT during the procedure.
- c. Performance of the ablation procedure on continuous, uninterrupted oral anticoagulation (e.g. no bridging with low molecular weight heparin) is required.
- d. In the event of persistent bleeding or cardiac tamponade, protamine may be administered to reverse heparin. If bleeding resolves, reversal of oral anticoagulant is not recommended.

8.4.4. Pulmonary Vein (PV) Ablation with the PFA system

- a. Deploy diagnostic catheters and perform transseptal puncture. Introduction of the [REDACTED] catheter should be performed according to the PFA system IFU.
- b. Every effort consistent with subject welfare should be made to treat all PVs or their anomalous equivalents.
- c. The [REDACTED] catheter will be advanced into the left atrium and tracked over the guidewire so that it is positioned at the entrance of the PV.
- d. Assess the catheter's spiral array positioning at the PV by fluoroscopy or other imaging technique. Reposition as needed.
- e. Map for pulmonary vein potentials.

- f. If desired due to proximity to phrenic nerve, deliver the test pulse while monitoring for stimulation of the diaphragm.

[REDACTED]

- h. Verify isolation of each pulmonary vein a minimum of 20 minutes after the last PFA application of the initial PVI in that PV. Each pulmonary vein should be minimally assessed for entrance block and, where assessable, exit block to demonstrate electrical isolation.
- i. Upon the Investigator’s assessment of procedure completion, Isoproterenol and/or adenosine may be used to assess pulmonary vein isolation.
- j. In the event of an inability to electrically isolate all accessible targeted pulmonary veins with the PFA system, any commercially released catheter deemed appropriate for the procedure may be used to complete the ablation procedure. Ablation using a non-study device to isolate any pulmonary vein will be considered a primary endpoint failure.

8.4.5. Other Ablations during Index Procedure

- a. Ablation of the cavotricuspid isthmus, with the goal of achieving bi-directional isthmus block, is recommended for subjects with a history of typical atrial flutter or inducible cavotricuspid isthmus dependent atrial flutter. It is recommended to attempt an induction of cavotricuspid isthmus dependent atrial flutter if the subject does not have a history of this arrhythmia. Any commercially released catheter deemed appropriate for the procedure may be used.
- b. Additional right atrial ablations may be performed if clinically necessary. Any commercially released catheter deemed appropriate for the procedure may be used.

8.4.6. Procedure Documentation

During the procedure, the following data will be collected:

- Catheters used
- Vein location for each PFA application (e.g. right superior PV)
- Use of test pulse or other phrenic nerve monitoring technique for each PFA application

- PFA therapy profile and electrode configuration used for each PFA application
- Procedural sedation methods/type, including any modifications to procedural sedation as a result of subject reaction to PFA applications
- Stimulation of diaphragm or skeletal muscle as a result of PFA applications
- Demonstrated electrical block and the device used to demonstrate
- Adjunctive catheters, mapping or visualization devices, procedure information, ACT, cardioversion use and fluoroscopy time will be collected; esophageal temperature may be collected

8.4.7. Cardioversion

Direct Current (DCCV) or pharmacological cardioversion may be considered at any point during the procedure when restoration of SR will assist in assessing the effectiveness of PFA or deemed necessary for the benefit of the patient. Electrical or pharmacological cardioversion to sinus rhythm must be attempted at the conclusion of the procedure if sinus rhythm was not restored.

8.4.8. Role of Medtronic Personnel at Study Procedure

Medtronic personnel will provide technical support at the ablation procedures under the supervision of a study investigator, but no data entry into the electronic database shall be performed by Medtronic personnel at sites. Medtronic personnel may support completion of the study worksheets. Medtronic personnel will collect procedural data from the PFA generator post-procedure via data download. It is the responsibility of the study site to ensure the subject is identified via subject ID number to prevent the distribution of personally identifiable information.

8.5. Hospital Discharge

At or shortly before hospital discharge, the following will be performed and collected:

- Adverse event assessment
- Review medications
- 12-lead ECG
- NIHSS Assessment
 - The NIHSS will be administered by study site personnel who have been certified to perform the NIHSS assessment and are delegated by their respective site to perform the assessment. The discharge NIHSS assessment will be conducted no earlier than the day following the procedure and no later than the subject's discharge. If the subject is discharged the same day as the ablation procedure, the NIHSS assessment will be conducted no earlier than 6 hours following the procedure. If the subject's discharge NIHSS total score is higher (worse) than the baseline NIHSS total score, a formal neurology consult will be initiated by the study site team to confirm the presence or absence of stroke or TIA. If the site's neurology team deems it necessary, imaging will be performed.

- Review study requirements with the subject to help ensure compliance with follow-up procedures.

[REDACTED]

8.6. Medications

Oral anticoagulation must be continued for at least two months post-ablation (e.g. no bridging post-ablation) for all subjects unless contraindicated. Decisions regarding the continuation of anticoagulation therapy more than two months following ablation should be based on the subject's risk factors for stroke as estimated by the CHA₂DS₂-VASc score and not on the presence or type of AF. Discontinuation of systemic anticoagulation therapy after two months post-ablation is not recommended in male subjects with a CHA₂DS₂-VASc score > 1 or female subjects with a CHA₂DS₂-VASc score > 2.

Information regarding medications prescribed for anticoagulation or to treat atrial arrhythmias will be collected from subject enrollment through study exit. The following information will be collected for medications to treat atrial arrhythmias: medication name, purpose for use, start and stop dates, dose, dosage changes (and reasons for changes), and route of administration. Data collection for anticoagulation medication will be limited to medication name and start and stop dates.

Requirements for use of antiarrhythmic medications are described below for the Paroxysmal AF and Persistent AF cohorts. Use of amiodarone is not permitted for any subject post-ablation. All other medications (those that are not specified below) are permitted in the study, with the exception of investigational drugs that may confound the study results. Beta-blockers may be prescribed per standard of care.

8.6.1. Paroxysmal AF Cohort

Per physician discretion, class I or III antiarrhythmic, including sotalol, medication use is permitted for up to 80 days following the ablation procedure. Prescriptions for these drugs should not allow a quantity that will last longer than 80 days post-procedure. It is recommended that site personnel contact subjects on day 80 post-ablation procedure to ensure they have stopped taking class I or III antiarrhythmic drugs. Class I or III antiarrhythmic drug use after the 90-day blanking period will be considered a primary endpoint failure.

8.6.2. Persistent AF Cohort

Up-titration of the Class I or III antiarrhythmic medication dose is allowed only in the 90-day post-procedure blanking period.

Class I and III antiarrhythmic medication use after the 90-day post-procedure blanking period:

- Subjects are allowed to remain on Class I or III antiarrhythmic medications at or lower than the historic maximum ineffective dose (prior to the ablation procedure) after the 90-day post-procedure blanking period.
- Re-initiation, at any point during follow-up, of a Class I or III antiarrhythmic medication that was failed or was not tolerated prior to the ablation procedure at any dose will be considered a primary endpoint failure.
- Initiation of a new Class I or III antiarrhythmic medication after the 90-day post-procedure blanking period will be considered a primary endpoint failure.
- Remaining on a dose higher than the historic maximum ineffective dose (prior to the ablation procedure) after the 90-day post-procedure blanking period will be considered a primary endpoint failure.

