- Acute procedural failure (see definition below)
- Documented AF/AT/AFL on Holter/patient activated ambulatory monitoring/12-lead ECG after the 90-day post-ablation blanking period
- Minimum of 30 seconds on Holter/patient activated ambulatory monitoring or 10 seconds on 12-lead ECG recording

	
 • Note: Documented occurrence and treatment of typical right-sided cavotricuspid isthmus dependent atrial flutter is not considered a failure. • Any subsequent AF surgery or ablation in the left atrium, except for repeat PVI ablations using PFA within the 90-day blanking period. • Direct current cardioversion for atrial tachyarrhythmia recurrences after the 90-day blanking period. • Class I or III antiarrhythmic drug (AAD) dose increase from the historic maximum ineffective dose (prior to the ablation procedure) or initiation of a new Class I or III AAD after the 90-day blanking period. Note: remaining on the same pre-ablation dose or decreased dose of a previously failed or not tolerated Class I or III AAD after the 90-day blanking is not considered a failure. 
Blanking period is defined as the first 90 days after the index ablation procedure. Recurrences of atrial arrhythmias during the blanking period will not be counted in the determination of the first clinical failure for the primary endpoint. Within the blanking period, recurrent arrhythmias can be managed with antiarrhythmic drugs or cardioversions. Titration of Class I and III antiarrhythmic medications are allowed during the blanking period.
 
Acute procedural failure is defined as:
 
 • Inability to isolate all accessible targeted pulmonary veins (minimally assessed for entrance block and, where assessable, exit block) during the index procedure • Ablation using a non-study device to isolate any pulmonary vein

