3.2. Purpose

The purpose of the study is to provide data demonstrating the safety and effectiveness of the PFA system for the treatment of atrial fibrillation. The study will also provide first in human insights into clinical safety and device function of the PFA system for pulmonary vein isolation as a treatment for AF. To this end, the clinical study has been designed into phases (Pilot and Pivotal), with each phase comprising a separate data set that will be analyzed and reported on per the below objectives.

The proposed indication for the PFA system evaluated in this Study is as follows:

The PFA system, which includes a compatible Medtronic multi-electrode cardiac ablation catheter, is indicated for the treatment of atrial fibrillation. The Medtronic multi-electrode cardiac ablation catheter is also intended to be used for cardiac electrophysiological (EP) mapping and measuring of intracardiac electrograms, delivery of diagnostic pacing stimuli and verifying electrical isolation post-treatment.

[REDACTED]

[REDACTED]

4. Objectives and Endpoints

Endpoint definitions for all study objectives are described in Section 12. [REDACTED]

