8.14. Assessment of Effectiveness

The Pilot Phase effectiveness objective is based on the data collected as discussed in Sections 4.1 and 12.1.

The Pivotal Phase primary effectiveness objectives are based on the data collected as discussed in Sections 4.2 and 12.2.

[REDACTED]

[REDACTED]

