Treatment success is defined as freedom from treatment failure. The study requires 24-hour Holter monitoring at 6 and 12 months in addition to weekly and symptomatic patient activated ambulatory monitoring transmissions from 3 through 12 months, and 12-lead ECGs at all follow up visits. Treatment failure is defined as any of the following components:

- Acute procedural failure (see definition below)
- Documented AF/AT/AFL on Holter/patient activated ambulatory/12-lead ECG after the 90-day post-ablation blanking period
- Minimum of 30 seconds on Holter/patient activated ambulatory or 10 seconds on 12-lead ECG recording
- Note: Documented occurrence and treatment of typical right-sided cavotricuspid isthmus dependent atrial flutter is not considered a failure.
- Any subsequent AF surgery or ablation in the left atrium, except for repeat PVI ablations using PFA within the 90-day blanking period.
- Direct current cardioversion for atrial tachyarrhythmia recurrences after the 90-day blanking period.
- Class I or III antiarrhythmic drug (AAD) dose increase from the historic maximum ineffective dose (prior to the ablation procedure) or initiation of a new Class I or III AAD after the 90-day blanking period. Note: remaining on the same pre-ablation dose or decreased dose of a previously failed or not tolerated Class I or III AAD after the 90-day blanking is not considered a failure.

Blanking period is defined as the first 90 days after the index ablation procedure. Recurrences of atrial arrhythmias during the blanking period will not be counted in the determination of the first clinical failure for the primary endpoint. Within the blanking period, recurrent arrhythmias can be managed with antiarrhythmic drugs or cardioversions. Titration of Class I and III antiarrhythmic medications are allowed during the blanking period.

Acute procedural failure is defined as:

- Inability to isolate all accessible targeted pulmonary veins (minimally assessed for entrance block and, where assessable, exit block) during the index procedure
- Ablation using a non-study device to isolate any pulmonary vein

Analysis Methods

The probability of a subject achieving effectiveness success at 12 months (365 days) will be estimated using survival analysis, the Kaplan-Meier method. The standard error will be approximated using Greenwood's formula. A two-sided 95% log-log confidence interval for the probability will be constructed.

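### Persistent arm: restarting a previously failed antiarrhythmic after day 90, at or below the historic maximum dose, is a primary endpoint failure in Section 8.6.2 but matches no failure component in Section 12.2.3

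*Combined protocol and SAP*

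**What the plan says.** Section 8.6.2 (Persistent AF Cohort) has four bullets under a lead-in about "Class I and III antiarrhythmic medication use after the 90-day post-procedure blanking period".

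- The first lets subjects stay on a Class I or III drug at or below the historic maximum ineffective dose.
- The second makes a failure of "Re-initiation, at any point during follow-up, of a Class I or III antiarrhythmic medication that was failed or was not tolerated" before ablation, whatever the dose.
- The third makes starting a new Class I or III drug after day 90 a failure.
- The fourth makes staying above the historic maximum dose after day 90 a failure.

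The persistent endpoint definition in Section 12.2.3 says that failure is any of its listed components. Its AAD component, which applies only once blanking has ended, is "dose increase from the historic maximum ineffective dose (prior to the ablation procedure) or initiation of a new Class I or III AAD". For that same period, a note exempts "remaining on the same pre-ablation dose or decreased dose of a previously failed or not tolerated Class I or III AAD". The synopsis carries the same component, beginning "Class I or III antiarrhythmic drug (AAD) dose increase from the historic maximum ineffective dose (prior to the ablation procedure".

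On which section governs, Section 4 states "Endpoint definitions for all study objectives are described in Section 12", and Section 8.14 states "The Pivotal Phase primary effectiveness objectives are based on the data collected as discussed in Sections 4.2 and 12.2".

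Section 8.8 makes electrical or pharmacological cardioversion after day 90 a failure. Section 12.2.3 lists only direct current cardioversion.

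**The concern.** Two sections of the same protocol give a different primary endpoint status to the same event. The persistent-arm effectiveness objective rests on one comparison, a lower confidence bound against 40%, in an unblinded single-arm study. An independent core lab adjudicates the arrhythmia component. The documents name no adjudicator for the AAD component, so the written rule has to settle the classification. If the mismatch is found only after the data have been seen, someone will have to choose between the two rules knowing which subjects each one affects.

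**Working it through.** **The two texts side by side (persistent arm, after day 90, no other failure event)**

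| Event | Section 8.6.2 | Section 12.2.3 and synopsis |
|---|---|---|
| Stays on old drug, at or below historic maximum | Allowed | Not a failure (note) |
| Starts a new drug | Failure | Failure |
| Restarts old drug above historic maximum | Failure | Arguably a failure (dose increase) |
| Restarts old drug at or below historic maximum | Failure | Not listed; the note does not mention restarts |
| Dose raised above historic maximum during blanking and kept | Failure (fourth bullet) | Unclear: the increase came before day 90 |
| Pharmacological cardioversion | Failure (Section 8.8) | Not listed |

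The fourth row is the conflict. It would disappear if a restart counted as starting a new drug, but 8.6.2 gives the two events separate bullets, so the protocol treats them as different.

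**The plan's own figure.** Inputs from Section 12.2.3: n = 150, 54% success at 12 months, 72% at 6 months, 2% acute failure, 5% uniform attrition, goal 40%, overall alpha 0.025, Kaplan-Meier with Greenwood standard error and log-log interval. The alpha split is redacted, so one look at one-sided 0.025 is assumed. A simulation with 10,000 replicates gives 91.5% power and 2.3% type I error. With a 98.0% one-sided bound, power is 90.1%. The stated 90% at 150 is reproduced to within two points.

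**How many subjects would change the result.** Without censoring, for x successes and S = x/150:

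se = sqrt((1 − S)/(150·S)) / |ln S|, and lower bound = S^exp(1.96·se).

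- x = 73: S = 0.4867, se = 0.08386/0.7202 = 0.1164, lower bound = 0.4867^1.256 = 0.4046. Passes.
- x = 72: S = 0.4800, se = 0.08498/0.7340 = 0.1158, lower bound = 0.4800^1.255 = 0.3981. Fails.
- Planned result: 0.54 × 150 = 81, lower bound 0.4570. Falling to 72 takes 81 − 72 = 9 subjects, or 9/150 = 6.0% of the arm.

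If the final one-sided alpha were 0.0225 or 0.02, the number stays at nine. At 0.015 it is eight, and at 0.0125 it is seven. Adding the plan's acute failures and attrition in a Kaplan-Meier simulation, the median number needed among passing trials is also nine (quartiles 6 and 13).

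**Range for the missing input.** The documents give no restart rate. Assume that 54% is the true rate under the 12.2.3 list, and that a share r of otherwise successful subjects restart an old drug at or below the historic dose after day 90. Under 8.6.2 the success rate becomes 0.54 × (1 − r):

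| r (assumed) | Success under 8.6.2 | Power at n = 150 |
|---|---|---|
| 1% | 53.5% | about 90% |
| 2% | 52.9% | about 87% |
| 5% | 51.3% | about 76% |
| 10% | 48.6% | about 53% |

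The lower rows illustrate the formula and are not forecasts.

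**The case against.** The best defence is that precedence is already settled: Sections 4 and 8.14 point to Section 12, so the analysis has one rule and 8.6.2 contains a stray sentence in a section on medication conduct. That is a fair reading, but it only identifies which text is wrong. The sentence in 8.6.2 declares a primary endpoint failure in plain terms, so if Section 12 governs it should go.

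A second defence is that 12.2.3 never calls a restart a success. This is correct: that status is inferred from silence, since the note exempts only remaining on a drug. One could then read a restart as a new initiation, with 8.6.2 spelling out the detail. The separate bullets in 8.6.2 make that reading unnatural.

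Third, the practical harm is limited. Nothing shows that sites classify the endpoint. They record drug name, purpose, dates, dose and dose changes (Section 8.6), and those data support either rule. Section 5.3 also promises a statistical analysis plan before data are analysed, which may derive the endpoint more fully. These points stand, and they reduce the likely effect. They do not reconcile the two texts.

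Fourth, the affected group is narrow. Most restarts prompted by recurrence would already fail on weekly and symptomatic transmissions, the two Holters or visit ECGs, and amiodarone is barred after ablation. This also stands.

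**Conclusion.** The inconsistency is real and concerns the primary endpoint. It is confined to persistent-arm subjects whose only event is a restart of a previously failed or not-tolerated Class I or III drug after day 90, at or below the historic maximum dose. Its effect is probably small and cannot be estimated from the documents. The figure of nine subjects rests on a planned result of 81/150, a single look at one-sided 0.025, and no censoring.

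A reader might infer more than the documents support:

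- *That 8.6.2 also fails restarts inside the blanking period.* Its wording on timing is loose, but the lead-in limits the list to use after day 90, and 12.2.3 allows drug management during blanking.
- *That the trial is underpowered or the sample size wrong.* The sample size is reproduced. The plan does not tie its 54% to either AAD rule, and the power losses above depend on assumed restart rates.
- *That sites will misclassify the endpoint.* No text gives them that task.

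The cardioversion mismatch in 8.8 is a minor instance of the same lack of alignment, since most such subjects would already fail on a documented arrhythmia. The change is worth making because it is nearly free now and would be awkward once results are known.

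**What to change.** Before outcome data are analysed, make Section 12.2.3 and the synopsis the full list of failure events, then adopt one of two rules. The choice is the sponsor's.

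- **(a) A restart is a failure.** Add to the persistent AAD component: re-initiation after the 90-day blanking period of a previously failed or not-tolerated Class I/III AAD, at any dose. In the second bullet of 8.6.2, limit the timing to after the 90-day blanking period.
- **(b) A restart at or below the historic dose is not a failure.** Delete the second bullet of 8.6.2 and extend the 12.2.3 note from remaining on a drug to remaining on or restarting it.

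Under either rule:

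- Carry the fourth bullet of 8.6.2 into 12.2.3 and the synopsis, so that a dose raised above the historic maximum during blanking and kept after day 90 is clearly a failure.
- State in both 8.8 and 12.2.3 whether pharmacological cardioversion after day 90 is a failure.

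A sensitivity analysis under the other classification is optional. The cost is wording in 8.6.2, 8.8, 12.2.3 and the synopsis. Section 8.6 already collects every data item needed.
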